## 13. STATISTICAL CONSIDERATIONS

### 13.1 Study Design/Description

This is a Phase IIB randomized, double blind clinical trial testing oral tamoxifen against 4-OHT gel in women with DCIS of the breast. A total of up to 108 women will be accrued from seven institutions, and randomized 1:1 (4-OHT gel: oral tamoxifen). Oral tamoxifen is the standard of care for medical therapy of DCIS, 4-OHT gel is expected to be as effective but less toxic, and therefore a randomized comparison is needed. The blinding will be maintained by the study statistician ([name]), who will develop the randomization schema and communicate directly with study pharmacies regarding subject assignment. Unblinding will occur for medical reasons if approved by the DCP study monitor ([name]).

## 13.2 Randomization/Stratification

We will consider the following strata: 1) Recruitment site, of which there will be seven, and 2) Pre- or post-menopausal status, within each site. A maximum of 108 participants with DCIS of the breast, newly diagnosed on core needle biopsy, will be accrued into two intervention arms: oral tamoxifen 20 mg daily, and 4-hydroxytamoxifen gel, 4 mg daily (2 mg to each breast). Due to early drop-out after randomization, we expect no more than 100 women to start intervention.

Of the women who start intervention, we assume an attrition of 20 women (20%) for study drop-out, or absence of residual DCIS in the surgical specimen, so that a total of 80 women (40 in the gel arm and 40 in the oral arm) will be evaluable for the primary study endpoint, and between 80 and 90 will be available for secondary endpoints. Assuming a screening rate of approximately 60 participants per month and an average accrual rate of 4.5 participants per month, we expect the recruitment to be complete within 24 months.

The patients will be enrolled at 7 centers:

- Northwestern University/Northwestern Medicine (NU)
- Duke University Medical Center (DUMC)
- Memorial Sloan Kettering Comprehensive Cancer Center (MSKCC)
- Cleveland Clinic Comprehensive Cancer Center (CCCCC)
- Mayo Clinic Rochester (MCR)
- St Elizabeth Hospital, Kentucky (SEH)
- University of Kansas Cancer Center (KUCC)

Randomization assignments will be provided for each combination of strata (site, meno status) in blocks of four. Excess blocks may be provided as it is not clear whether meno/post meno strata will be balanced.

## 13.3 Accrual and Feasibility

13.3.1 Sample Size: We plan to accrue up to 108 subjects over 24 months. Therefore the monthly rate in the base period is 4.5. The distribution across institutions may be revised as the study progresses. The last participant will go off-treatment in month 27, and complete 30-day follow-up in month 28.

13.3.2 Gender distribution: will be entirely female. Although men do develop DCIS, the number is extremely small and it is unlikely that any men with DCIS will be seen at the recruiting sites over an 18 month period. Furthermore, the skin permeation characteristics of 4-OHT gel has never been studied in men, and may be different given different skin thickness in men and women. Finally, the target population for the study intervention is exclusively women; breast cancer prevention therapy for men is not a practical objective at this time.

13.3.3 Minority populations will be recruited actively. Minority populations at each site are

- NU, 25.6% of the DCIS population are of non-European ancestry (18% African, 4% Hispanic, 3.5% other).
- Duke has high fractions of African American women with DCIS (24%).
- At Cleveland Clinic, 18% of DCIS patients are AA, 4% other minorities, 78% European American (EA).
- At MSKCC, during 2014, DCIS patients were: 73% EA, 24% minority (12% black, 6% Asian, 6% Hispanic), 4% other or unknown.
- Mayo Rochester has a largely European-American population.
- St Elizabeth's Kentucky also has a largely European-American population.
- At KUCC, approximately 13% of DCIS patients are African American, 1% Hispanic, 1% Asian, and the rest are European-American.

## 13.4 Primary Objective, Endpoint(s) and Analysis Plan

### 13.4.1 Hypothesis and Primary Objective:

We hypothesize that the application of 4-OHT gel to the breast at a dose of 2 mg per breast daily will result in a decrease in the Ki-67 labeling index of DCIS lesions that is comparable to the decrease seen with use of oral TAM. Further, that this will occur with 4-OHT concentrations in the breast that are significantly higher than circulating levels. The primary objective of this study is to demonstrate that topical transdermal 4-OHT is not inferior to oral tamoxifen in decreasing Ki-67 labeling index (LI) of DCIS lesions. In the control (oral TAM) group we expect the mean relative decrease in Ki-67 LI in the surgical specimen to be 50% compared to the diagnostic core biopsy samples after therapy. In the study agent group we will accept a relative mean decrease of at least 35% as evidence of non-inferiority.

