### 13.4.2 Proposed Sample Size:

A total of up to 108 women will be accrued and randomized over an 18 month period (1:1 oral:gel), with no more than 100 women to start intervention. Assuming a 20% rate of nonevaluable samples due to insufficient residual DCIS, we expect a total of 80 subjects evaluable for the primary endpoint of Ki67, comparing pre to post-therapy samples. Primary analysis will be conducted in all randomized evaluable patients per intent-to-treat. Additional analyses will be conducted in the per-protocol population of patients who were treatment-compliant as defined in Section 5.7. Adverse events will be evaluated in all patients who received at least one treatment dose.

Sample size calculations: From previous publication (Table 2, Lee et al.) we have an average percent staining for Ki67 at baseline of 7.5% with  $SD=5.4\%$ . Assuming within-subject correlation between pre- and post-treatment values is  $\rho=0.5$ , the pooled  $SD$  of the changes will be  $SD_p=5.4\%$ . A 50% drop (from 7.5%) gives 3.75% while a 35% drop (from 7.5%) gives 4.9% in Ki67 staining. If the drop in the 4-OHT group is non-inferior to the standard of care, we would see it. We use compatible  $SD$  from Table 2 in Lee et al, obtaining for the 4-OHT group adequate power to detect a non-inferiority of 35% or bigger drop with a small type 1 error of 10%. Now 2.6% staining. Thus, with a non-inferiority margin  $M=2.6\%$ , sample size of  $n=40$  evaluable patients per arm will provide 80.5% power with one-sided  $\alpha = 0.10$  significance level to detect non-inferiority based on a two-sample equal variance t-test comparing changes in Ki67% staining. Calculations were done using PASS 11.

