### 13.4.3 Statistical analysis plan for primary endpoint:

The primary objective is to estimate and compare changes in %Ki-67 expression from the pre-treatment specimen to the post-treatment specimen between women who received oral Tamoxifen + placebo gel compared with those who receive 4-OHT gel + oral placebo. When using a continuous outcome measured at baseline and after treatment in a randomized trial, it is recommended to use an analysis of covariance (ANCOVA) to model[55, 56]). In addition, the two-sample t-test comparing the change score  $Y_1 - Y_0$  vs.

treatment is prone to incorrect interpretations if the correlation between  $Y_1$  and  $Y_0$  is high, and the ANCOVA model is preferred in this instance.

In this study, we will use the model  $Y_1 = \alpha + \beta Y_0 + \gamma G + \epsilon$ , where  $Y_1$  and  $Y_0$  are the post- and pre-treatment %Ki-67 expression, and  $G = 0$  or  $1$  indicates whether the subject belongs to the treatment (4-OHT) or the active control group. This model will be used to test whether the difference between treatment arms ( $\gamma$ ) exceeds the pre-specified non-inferiority margin by testing  $H_0: \gamma \geq M$  v.s.  $H_1: \gamma < M$ , where  $M=2.6\%$  is the pre-specified non-inferiority margin. In order to perform such test, we will modify the outcome as  $Y_1^* = Y_1 - M$  when  $G = 1$ , or  $Y_1^* = Y_1$  otherwise. Thus, the model becomes  $Y_1^* = \alpha + \beta Y_0 + \gamma^* G$ , and  $\gamma^* = \gamma - M$ . This corresponds to the hypothesis tests  $H_0: \gamma^* \geq 0$  v.s.  $H_1: \gamma^* < 0$ , which can be obtained from the standard regression model output in a software package. The model will also adjust for the stratification variable menopausal status. The above-described ANCOVA model is different from the non-inferiority test used for the power analysis; however, the power for the ANCOVA models is likely to be greater than power for a t-test comparing change scores [57]. %Ki-67 expression may be transformed (e.g. using log-transformation) to satisfy the normality assumption.

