### 13.5.4 Analysis Plan for Secondary Endpoints:

Secondary outcomes will be summarized by

treatment arm using descriptive statistics, including mean and confidence interval, or median and interquartile range for continuous outcomes, and proportions and confidence intervals for categorical variables. Outcomes will be compared between arms, with two main types of analyses being conducted: noninferiority testing and testing for differences between arms, depending on the specific hypotheses for each outcome. **Noninferiority analyses.** Similar to the primary outcome, we expect changes in secondary efficacy outcomes (Oncotype DCIS-Score) to be similar (noninferior) in the 4-OHT gel arm vs. oral tamoxifen arm. Because preliminary data necessary for setting noninferiority margins are not available for all endpoints, we will use a strategy similar to how the non-inferiority margin was set for the primary endpoint, i.e. we will set the margin  $M$  to correspond to a 35% change from the average baseline value observed among all patients (i.e. pooling across both study arms). These biomarkers will be compared between arms using ANCOVA models similar to those described for the primary endpoint, with post-treatment measurement as the outcome variable, and with treatment arm and baseline value as predictors, and testing  $H_0: \gamma \geq M$  vs.  $H_1: \gamma < M$  as described above. **Treatment differences.** Continuous endpoints for which treatment differences are expected post-treatment (breast and plasma levels of TAM and its metabolites; plasma proteins involved in coagulation; plasma markers of systemic estrogenic effect; and BESS questionnaire) will be compared between arms using a two-sample t-test. Normality assumption will be checked, and data may be transformed (e.g. logarithmically) to satisfy the normality assumption. If no suitable transformation can be found, groups will be compared using the Wilcoxon ranksum test. Additional exploratory analyses will include linear regression models and will adjust for additional covariates. Outcomes for which changes are expected to be different between arms will be analyzed using ANCOVA models as described for the primary endpoint, but testing whether the treatment effect is 0 rather than the non-inferiority margin  $M$ , i.e.  $H_0: \gamma = 0$  vs.  $H_1: \gamma \neq 0$ . These tests will be two-sided. Tests of these pre-specified hypotheses will not be adjusted for multiple comparisons, and will be interpreted accordingly.

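### The 2.6-point margin is 35% of baseline, not the 1.125-point gap between a 50% and a 35% drop, so the primary test and its 80.5% power do not address the protocol's 35% criterion

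*Combined protocol and SAP*

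**What the plan says.** Section 13.4.1 expects a mean relative decrease of 50% on oral tamoxifen and continues: "In the study agent group we will accept a relative mean decrease of at least 35% as evidence of non-inferiority".

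Section 13.4.2 takes an "average percent staining for Ki67 at baseline of 7.5% with" an SD of 5.4% and converts the two drops to staining: "A 50% drop (from 7.5%) gives 3.75% while a 35% drop (from 7.5%) gives 4.9% in Ki67 staining". It describes the design as having "adequate power to detect a non-inferiority of 35% or bigger drop with a small type 1 error of 10" percent. It then introduces 2.6% staining without deriving it, sets M = 2.6%, and states that 40 "evaluable patients per arm will provide 80.5% power with one-sided" alpha of 0.10.

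Section 13.4.3 tests the ANCOVA treatment coefficient against the same 2.6% and adds that "Ki-67 expression may be transformed (e.g. using log-transformation) to satisfy the normality assumption". It gives no margin for a transformed scale.

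Section 13.5.4 shows where 2.6 probably came from. For the secondary non-inferiority endpoints, "we will use a strategy similar to how the non-inferiority margin was set for the primary endpoint", with the margin chosen "to correspond to a 35% change from the average baseline value observed among all patients".

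**The concern.** A non-inferiority margin is the largest loss against the control that will be tolerated. If tamoxifen is expected to give 50% and the gel must give at least 35%, the tolerable loss is 15 percentage points of baseline, or 1.125 staining points. The plan appears to have taken the minimum acceptable gel effect (35% of baseline) and used it as the maximum tolerable difference between arms.

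This is the primary hypothesis test. A reader of section 13.4.1 would take success to mean that the gel lowers Ki-67 by at least 35%. The test as written rules out something much weaker. The quoted power and type 1 error are also attached to a criterion that they do not describe.

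**Working it through.** **Inputs** (sections 13.4.1 and 13.4.2): baseline mean 7.5; baseline SD 5.4; pre/post correlation 0.5; SD of change √(2 × 5.4² × (1 − 0.5)) = 5.4; n = 40 per arm; one-sided alpha 0.10; M = 2.6. The plan does not state the true difference assumed for power. Zero reproduces its figure and is used below.

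**1. The plan's own figure.** SE = 5.4 × √(2/40) = 1.207. With 78 degrees of freedom the critical t is 1.2925 and the noncentrality is 2.6/1.207 = 2.153. Power is 80.5%, as stated.

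**2. The margin that the 35% criterion implies.** 7.5 × 0.50 = 3.75 and 7.5 × 0.65 = 4.875, a gap of 1.125 (1.15 with the plan's rounded 4.9). By contrast, 0.35 × 7.5 = 2.625, which rounds to 2.6. The ratio is 2.6/1.125 = 2.3.

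**3. What M = 2.6 excludes.** The null boundary for the gel drop is (7.5d − 2.6)/7.5, where d is the true tamoxifen drop.

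| Tamoxifen drop | Gel drop at the boundary |
|---|---|
| 50% | 15.3% |
| 40% (assumed) | 5.3% |
| 35% (assumed) | 0.3% |

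At d = 50% the gel keeps (3.75 − 2.6)/3.75 = 31% of the tamoxifen effect. The 35% criterion keeps 35/50 = 70%. The margin is fixed in points, so if tamoxifen achieves only about 35%, an inert gel sits at the boundary.

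**4. Operating characteristics at n = 40 per arm.** The ANCOVA residual SD is 5.4 × √(1 − 0.5²) = 4.68, with 77 degrees of freedom.

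| Quantity | t-test on change | ANCOVA |
|---|---|---|
| Power at M = 1.125, true difference 0 | 36% | 42% |
| Same, correlation 0.3 to 0.7, both SDs 5.4 | 31–47% | 38–51% |
| Pass rate at M = 2.6, gel truly at a 35% drop | 47% | 55% |
| Pass rate at M = 2.6, gel truly at a 15.3% drop | 10% | 10% |
| n per arm for 80% power at M = 1.125 | 209 | 157 |

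Alpha therefore holds at a true gel drop of about 15%. At a true drop of 35% the pass rate is 47–55%, not 10%.

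**5. Smallest observed gel drop that passes, if tamoxifen shows 50%.** The largest passing difference is M − t × SE. At M = 2.6 this is 2.6 − 1.2925 × 1.207 = 1.04 (t-test) or 1.25 (ANCOVA), an observed gel drop of 36% or 33%. At M = 1.125 it is −0.44 or −0.23, an observed gel drop of 56% or 53%.

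**6. Log scale.** The 35% rule becomes a ratio of geometric means of 0.65/0.50, and ln(1.3) = 0.262. This equals the 35% rule only if tamoxifen achieves 50%. ANCOVA power then depends on the post-treatment variance:

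- If the CV stays at 5.4/7.5 = 0.72, the log SD is 0.646 and power is about 79% at correlation 0.5.
- If the post-treatment SD is 5.4 around a mean of 3.75 (CV 1.44), the log SD is 1.06 and power is about 50% (45–60% for correlation 0.3 to 0.7).

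The gain comes from the variance assumption and not from the log. In lognormal simulation, raw M = 1.125 also has about 79% under constant CV, and about 49% with a post-treatment SD of 5.4.

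**7. Secondary endpoints.** A margin of 35% of baseline places an inert gel inside the margin for any marker that tamoxifen lowers by less than 35%. Using the primary endpoint's baseline, SD and n as an illustration, an inert gel passes 11% of the time if tamoxifen lowers the marker by 34%. If tamoxifen lowers it by 20%, the gel passes 36% (t-test) or 42% (ANCOVA) of the time.

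**The case against.** The strongest reply is that 35% was meant as an observed result and not as a null boundary. Section 13.4.1 speaks of accepting a decrease as evidence, and step 5 shows that M = 2.6 passes at an observed gel drop of 33–36% when tamoxifen shows 50%. On that reading the test behaves roughly as described and the fault is unclear wording. This narrows the point but does not remove it. No section says that 35% is an observed threshold, section 13.5.4 points to a different origin for the margin, and the null being tested still excludes only true drops below about 15%.

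A second reply is that this is a Phase IIB trial, that M = 2.6 is pre-specified and consistent between sections 13.4.2 and 13.4.3, and that how much tamoxifen effect to retain is a design judgement. That is fair. A wide margin can be defended, but the plan must then present it as one.

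Third, the loss of power depends on the variance model. The 36–42% assumes normal data with the plan's SD, and the figure would be near 79% if the CV stayed constant after treatment. This stands, and it is why the restated power should name its variance assumption. The boundary calculation does not depend on the SD.

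Finally, the wording in section 13.4.3 that defines the group indicator could be read as coding the control as 1. The working takes the gel as 1, the coding under which the stated hypotheses test non-inferiority of the gel.

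**Conclusion.** The concern holds. The margin used for power and testing is 2.3 times the one implied by the protocol's 50% and 35% figures. With a 7.5% baseline and a true tamoxifen drop of 50%, success would rule out gel drops below about 15%, and below less than that if tamoxifen does worse. The 80.5% power is right for M = 2.6. For the margin that the 35% criterion implies, it is about 36% (t-test) or 42% (ANCOVA) on the plan's SD, correlation 0.5 and normal data. If 35% was meant as an observed threshold, the plan needs to say so. The missing log-scale margin and the secondary margins in section 13.5.4 are related gaps. The main conclusion does not depend on them.

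**What to change.** Settle this before any Ki-67 result is available by arm. Blinding alone is a weak safeguard, because the study statistician holds the unblinded randomization log (section 6.8) and manages the data (section 12.1). Choose one of two routes:

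- **(a) Keep M = 2.6.** Remove the 35% criterion from sections 13.4.1 and 13.4.2, or state that it is an observed value and not the null boundary. State that success excludes only gel drops below about 15% if tamoxifen achieves 50%.
- **(b) Set M = 1.125.** Restate power as about 36–42% on the plan's SD. At this sample size the gel would need an observed drop of 53–56% against 50% on tamoxifen, so (a) is the more practical route.

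If a log transform stays allowed, pre-specify its margin (for example 0.262 as a log ratio of geometric means), how zeros are handled, and the power with its variance assumption. The post-treatment SD from the sponsor's prior DCIS trial (18 evaluable women, section 2.3.2) could inform that choice.

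In section 13.5.4, set the secondary margins on the corrected basis, or report differences with confidence intervals and make no non-inferiority claim.

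The cost is revised wording, a restated power figure, and amendment approval by DCP and the Central IRB (section 14.3). Neither route needs extra patients. Route (b) means accepting the lower power at 40 per arm.

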### 13.4.2 Proposed Sample Size:

A total of up to 108 women will be accrued and randomized over an 18 month period (1:1 oral:gel), with no more than 100 women to start intervention. Assuming a 20% rate of nonevaluable samples due to insufficient residual DCIS, we expect a total of 80 subjects evaluable for the primary endpoint of Ki67, comparing pre to post-therapy samples. Primary analysis will be conducted in all randomized evaluable patients per intent-to-treat. Additional analyses will be conducted in the per-protocol population of patients who were treatment-compliant as defined in Section 5.7. Adverse events will be evaluated in all patients who received at least one treatment dose.

Sample size calculations: From previous publication (Table 2, Lee et al.) we have an average percent staining for Ki67 at baseline of 7.5% with  $SD=5.4\%$ . Assuming within-subject correlation between pre- and post-treatment values is  $\rho=0.5$ , the pooled  $SD$  of the changes will be  $SD_p=5.4\%$ . A 50% drop (from 7.5%) gives 3.75% while a 35% drop (from 7.5%) gives 4.9% in Ki67 staining. If the drop in the 4-OHT group is non-inferior to the standard of care, we would see it. We use compatible  $SD$  from Table 2 in Lee et al, obtaining for the 4-OHT group adequate power to detect a non-inferiority of 35% or bigger drop with a small type 1 error of 10%. Now 2.6% staining. Thus, with a non-inferiority margin  $M=2.6\%$ , sample size of  $n=40$  evaluable patients per arm will provide 80.5% power with one-sided  $\alpha = 0.10$  significance level to detect non-inferiority based on a two-sample equal variance t-test comparing changes in Ki67% staining. Calculations were done using PASS 11.

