### 3. SUMMARY OF STUDY PLAN

**3.1 Study design:** We propose a randomized, double-blind, placebo-controlled pre-surgical trial of 0.228% 4-hydroxy-tamoxifen (4-OHT) gel vs. oral tamoxifen (TAM) 20 mg daily in up to 108 women with a core needle biopsy diagnosis of ER positive DCIS, regardless of grade, with 1:1 randomization to oral TAM and 4-OHT gel. We will consider the following strata: 1) Recruitment site, of which there will be seven, and 2) Pre- or post-menopausal status, within each site. The 4-OHT group will apply active gel 2 mg daily to each breast and take oral placebo for a minimum of 4 and a maximum of 10 weeks. The TAM group will take 20 mg TAM orally daily and apply gel placebo daily to each breast for 4 to 10 weeks. The primary endpoint is Ki67 labeling index in the DCIS core (pre-therapy sample) compared to the surgical sample (post-therapy sample), with the expectation that the reduction in this parameter will be equivalent in the two arms.

**3.2 Number of participants to be enrolled:** A maximum of 108 participants with estrogen receptor (ER) positive DCIS of the breast, newly diagnosed on core needle biopsy, will be accrued into two intervention arms: oral tamoxifen 20 mg daily, and 4-hydroxytamoxifen gel, 4 mg daily (2 mg to each breast). Due to early drop-out after randomization, we expect no more than 100 women to start intervention. In addition, we assume that there will be an attrition of 10 women (10%) related to lack of compliance to medication or other logistical reasons, and an attrition of another 10 women (10%) related to lack of sufficient DCIS tissue for analysis of the primary endpoints. Therefore a total of 90 women (45 in gel arm and 45 in oral arm) will be evaluated for study endpoints, and 80 women (40 per arm) will provide data for the primary endpoint. Assuming a screening rate of approximately 60 participants per month and an average accrual rate of 4.5 participants per month, we expect the study to be complete within 24 months. Accrual is competitive and sites should accrue as many participants as possible until total accrual is met.

**3.3 The study population:** newly diagnosed adult DCIS patients will be enrolled at 7 centers. Eligible participants will be approached following diagnostic core needle biopsy at the time of initial surgical consultation. The centers are:

- Northwestern University/Northwestern Medicine (NU)

- Duke University Medical Center (DUMC)

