## **5.7 Adherence/Compliance**

5.7.1 Participants will be considered compliant if they have taken 80% of the prescribed doses and have missed no more than 3 doses in the final 14 days prior to surgery.

5.7.2 The participants will be asked at registration if they would like to utilize a phone application in place of paper forms. According to subject preference, participants will either utilize phone application or fill out paper forms daily to monitor compliance. For participants utilizing the phone application, the study coordinator will be notified after 2 days of missed entries. For individuals using paper forms, email messages will be sent daily for the first week; in following weeks, messaging will be targeted to women having difficulty remembering their dose.

5.7.3 Capsule counts and weighing of gel dispensers will be performed at the conclusion of therapy. Drug and metabolite levels will be measured in blood and tissue on the last day of administration. Prescribed doses include one capsule per day, or one pump of the gel on each breast per day. If the capsule count consumed by the subject is lower than  $D*80\%$ , or the amount of gel consumed is less than  $2D*80\%*[m - sd(m)]$ , where D is the number of days between visits, m and  $sd(m)$  are the mean and standard deviation of the weight of one pump of the gel provided by the manufacturer, or if more than three doses of therapy are missed during the final 14 days, the subject will be considered non-compliant. For subjects with only one breast, the lower limit of the amount of gel consumed for compliance is  $D*80\%*[m - sd(m)]$ . All participants who receive a study agent for any period of time will be evaluable for toxicity. Treatment compliance assessment will be based on the active ingredient component of the treatment regimen, i.e. the pill count for the Oral Tamoxifen group and gel dispenser weight for the 4-OHT gel group.

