### **8.4 Off-Study Criteria**

8.4.1 Participants may go “off-study” for the following reasons: completed the protocol-prescribed intervention, AE or serious adverse event, lost to follow-up, inadequate agent supply, noncompliance, concomitant medications, medical contraindication/pregnancy, withdraw consent, determination of ineligibility (including screen failure), death, or investigator’s discretion. Participants will continue to be followed, if possible, for safety reasons. Participants who stop agent within 6 days of surgery will continue their study visits to collect endpoint data according to the schedule of events, unless the participant withdraws consent for further study procedures.

8.4.2 For the primary analysis (intent to treat, ITT) any participant that received study agent and has tissue available will be included. A per protocol analysis will then be completed which removes noncompliant participants or participants who went off study prior to 4 weeks. For these analyses, participants who complete 4 weeks of study agent will be considered evaluable.

8.4.3 Pregnancy would be considered a medical contraindication to continued use of the study agents. If a pregnancy occurs, the patient will be followed through the resolution of the pregnancy and the outcome of the pregnancy will be recorded. Some pregnancy outcomes are considered to be an SAE (e.g. miscarriage, birth defect) and must be reported following the SAE procedures in section 11.

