### 13.8 Evaluation of Response

13.8.1 *Intent to treat analysis* All samples from all subjects who receive drug will be evaluated and included in the primary analysis, which will be based on intent to treat principle. Per protocol analyses will then be performed as described in Section 8.4.2.

13.8.2 *Missing data* The general approach will be to perform a complete case analysis when the missingness rate is low, and when a missing completely at random (MCAR) or missing at random (MAR) assumption can be reasonably made. To determine whether such assumptions are reasonable, reasons for data missingness will be documented, and clinical and demographic characteristics will be compared between patients with and without missing data for each particular endpoint. If the missing data rate is relatively high but the MAR assumption is reasonable, complete case analyses will be done and carefully interpreted given high missing data rates. To assess the robustness of findings, sensitivity analyses will be performed, including covariate-adjusted regression models, and “best-worst” analyses where all missing values are replaced by either best or worst values for categorical outcomes, and by highest or lowest observed values for continuous outcomes. Multiple Imputation. If data is missing for > 10% of the entries, multiple imputation may be performed via a semiparametric approach based on association between continuous biomarker variables, between binary variables, and between continuous with binary and categorical data [see refs 52-55]. In these approaches, missing data are filled in by plausible values obtained from joint modeling. Observed data are first transformed to normally distributed values so as to satisfy the normality assumptions of the joint modeling approach. Imputed data are then transformed back onto the original scale of the observed data. Imputations are run until convergence criteria are met depending on pairwise correlations between the variables imputed. Performance of the multiple imputation will be assessed via standardized biases (< 50% being acceptable), coverage rates (> 90% being acceptable), small root mean square errors, and average widths of 95% confidence intervals for the estimates from imputed data being comparable to the widths of 95% confidence intervals for the original data pertaining to the pairwise correlations. The goal for the imputed data is to satisfy the assumptions from our power analysis and ensure the convergence of parameter estimation.

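### Non-inferiority is concluded from the intent-to-treat set alone; the planned per-protocol analysis has no role in the conclusion, and no rule covers disagreement between the two

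*Combined protocol and SAP*

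**What the plan says.** The primary analysis set is described in three places. Section 13.4.2: "Primary analysis will be conducted in all randomized evaluable patients per intent-to-treat". Section 8.4.2: "For the primary analysis (intent to treat, ITT) any participant that received study agent and has tissue available will be included". Section 13.8.1: "All samples from all subjects who receive drug will be evaluated and included in the primary analysis, which will be based on intent to treat". All three amount to a modified ITT set: dosed women with usable tissue.

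The per-protocol analysis comes second each time. In Section 13.4.2 it is additional: "Additional analyses will be conducted in the per-protocol population of patients who were treatment-compliant as defined in Section 5.7". In Section 8.4.2 it follows the primary analysis: "A per protocol analysis will then be completed which removes noncompliant participants or participants who went off study prior to 4 weeks". Section 13.8.1 refers back to 8.4.2. The two definitions differ. Section 13.4.2 uses compliance alone, while 8.4.2 also removes women who left the study before 4 weeks.

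Compliance is defined in Section 5.7: "Participants will be considered compliant if they have taken 80% of the prescribed doses and have missed no more than 3 doses in the final". The window meant there is the last two weeks before surgery. Compliance is judged on the active component, by capsule count in the oral arm and by gel weight in the gel arm.

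The test in Section 13.4.3 compares the arm difference with M = 2.6 points and names no second analysis set. On expected losses, Section 3.2 says: "we assume that there will be an attrition of 10 women (10%) related to lack of compliance to medication or other logistical reasons".

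**The concern.** In a superiority trial, women who do not take their drug usually make success harder, so ITT is the cautious choice. In a non-inferiority trial the effect can run the other way. If women in both arms, or mainly in the oral arm, go without drug, the arms look more alike and the gel passes more easily. For that reason a per-protocol analysis is normally read alongside ITT.

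Here both analyses are planned, but only one counts. The primary objective concerns the reduction in Ki-67 that the gel produces, which reads most naturally as a drug effect, yet the plan never says whether the target is the effect as assigned or the effect under adherence. If ITT passes and per-protocol fails, the text leads to a non-inferiority claim, and any other handling would be decided after the results are known.

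**Working it through.** **Inputs from the documents.** M = 2.6; Ki-67 SD 5.4; pre-post correlation 0.5; 40 evaluable women per arm; one-sided alpha 0.10 (Section 13.4.2). Baseline mean is 7.5 and the expected oral drop is 50%, which is 3.75 points (Sections 13.4.1 and 13.4.2).

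**Assumptions.** The documents give no non-adherence rate among analysed women, so a fraction f of 5, 10 and 20% is used. Non-adherers are first taken to have no drug effect, which is the extreme case.

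**Step 1: reproduce the plan's figure.** SD of change = sqrt(2 × 5.4² × (1 − 0.5)) = 5.4. Standard error = 5.4 × sqrt(2/40) = 1.207. Noncentral t with 78 df and noncentrality 2.6/1.207 = 2.153 gives power 80.5%, as stated. For the planned ANCOVA, residual SD = 5.4 × sqrt(1 − 0.5²) = 4.68, and power is 88.3%.

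**Step 2: false-claim rate for the effect in adherent women, ITT alone.** Let the true gel deficit in adherent women equal M: oral drop 3.75, gel drop 3.75 − 2.6 = 1.15. The difference D seen in the ITT set is then:

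- balanced non-adherence: D = 2.6 × (1 − f)
- oral arm only: D = 2.6 − 3.75f
- gel arm only: D = 2.6 + 1.15f

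The chance of declaring non-inferiority comes from the noncentral t with noncentrality (2.6 − D)/SE. At 10% balanced, D = 2.34 and the noncentrality is 0.26/1.207 = 0.215.

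| Non-adherence | 5% | 10% | 20% |
|---|---|---|---|
| Balanced, t-test | 12.0% | 14.3% | 19.7% |
| Balanced, ANCOVA | 12.3% | 15.1% | 21.6% |
| Oral arm only, t-test | 13.0% | 16.5% | 25.3% |
| Gel arm only, t-test | 9.2% | 8.4% | 7.1% |

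If non-compliant women keep half the arm difference, 10% balanced gives 12.0% (t-test). If they keep three quarters, it gives 11.0%.

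**Step 3: require both sets to meet M.** This was simulated with the per-protocol women nested in the 40 per arm (38, 36 and 32 per arm) and balanced non-adherence unrelated to outcome. The false-claim rate in Step 2's setting falls to about 9% at both 10% and 20%. In these simulations ITT passes while per-protocol fails in roughly 5% of trials at 10% non-adherence and roughly 10% at 20%.

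| Joint power, no true difference | 5% | 10% | 20% |
|---|---|---|---|
| t-test (ITT alone 80.5%) | 77% | 75% | 71% |
| ANCOVA (ITT alone 88.3%) | 86% | 84% | 80% |

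If each woman's compliance is instead random and non-adherers lose the whole Ki-67 drop, the extra variance lowers the t-test row to about 76, 74 and 69%.

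**The case against.** Three stronger readings are tempting, and the documents support none of them.

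- *That the stated 10% error rate is wrong.* It is not. Section 13.4.3 tests the arm difference in the analysed set, and for that quantity the 10% holds. An excess appears only when the target is the effect in women who take the drug.
- *That false claims always become more likely as adherence worsens.* The direction depends on the arm. With gel-only non-adherence the arms move apart and the rate falls below 10%.
- *That the plan itself expects 10% non-compliance in the primary set.* Section 3.2 subtracts those women before arriving at 80 evaluable, and its 10% also covers logistical losses.

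The plan also keeps many women without a drug effect out of the analysis. Section 3.8 measures endpoints after early surgery only beyond 4 weeks of therapy, and Section 8.4.2 ties evaluability to completing 4 weeks. Under Section 5.7, missing a little over 20% of doses, or four in the last 14 days, makes a woman non-compliant, so many such women would be partial takers.

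This limits the size of the problem but does not remove it. Sections 8.4.2 and 13.8.1 still admit dosed women with tissue whatever their compliance. Section 8.3 continues endpoint collection in women who stop within 6 days of surgery, some of whom would fail the 14-day rule. The per-protocol definition presupposes that such women exist.

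Per-protocol is not a clean standard either. It drops women after randomization, using a different compliance measure in each arm, so its error rate is nominal only if compliance is unrelated to outcome. It could also be said that both results would be published and readers could judge for themselves. That does not settle what the trial concludes.

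**Conclusion.** The gap is real: the only primary claim rests on one set, the second planned set has no say, and disagreement is not covered. This merits a change to the plan, but it is not an error in the stated alpha or power.

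The size is conditional. For the effect in adherent women, the false-claim rate runs from about 12 to 20% (t-test) or 12 to 22% (ANCOVA) at 5 to 20% balanced non-adherence, and up to about 25% if non-adherence is confined to the oral arm. It is 7 to 9% if confined to the gel arm. These figures rest on assumed rates and on no drug effect in non-adherers; partial adherence gives smaller excesses.

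**What to change.** In Sections 13.4.2, 8.4.2 and 13.8.1:

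1. State whether the target is the effect as assigned or the effect under adherence.
2. Use one per-protocol definition, reconciling 13.4.2 with 8.4.2.
3. Conclude non-inferiority only if the one-sided 90% upper confidence limit is below M in both sets. If they disagree, report the primary result as inconclusive.
4. Note that per-protocol excludes women after randomization, so neither set suffices alone.
5. Beside the 80.5%, report joint power over an assumed range of non-adherence, as tabulated above.

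Both analyses are already planned, so only wording changes; no further women or data are needed. The price is power relative to ITT alone: about 3 to 10 points on the t-test calculation, and about 2 to 8 on the planned ANCOVA, for 5 to 20% balanced non-adherence. The rule should be fixed before results are known.
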